as the Screening assessment as long as the exam was performed within 21 days prior to the first dose of study drug. Dermatologic examination may be performed up to 7 days prior to the corresponding study visit or post dose at the study visit. See [Section 6.11.6](#) for further details.

15. Ophthalmologic examination will be performed at Screening and if clinically indicated during treatment with study drug. This examination does not have to be repeated if there is documentation of an examination that met protocol criteria within 28 days before the Screening Visit and after the last dose of previous anticancer treatment.
16. The EORTC QLQ-C30 and EQ-5D-5L questionnaires must be performed before the patient sees the Investigator or designee on the day of the scheduled visit. If the dermatologic examination or imaging assessments are completed within 7 days of the scheduled visit and the patient does not see the Investigator or designee, the questionnaires do not need to be completed on that day. The EORTC QLQ-C30 will be performed prior to the EQ-5D-5L, followed by the Healthcare Utilization Questionnaire. Questionnaires are collected via an electronic patient reported outcome system on provided tablet computers.
17. Patients should be instructed to take the study drug at approximately the same time each day. On days of planned study visits, patients will be informed to take the study drug at the study site after predose assessments are completed.
18. At the time of dose escalation, the patient must come to the site for study drug to be dispensed.
19. PK sampling will be performed at the following time points: Cycle 1 Day 1 predose and 6 hours after dosing, Cycle 1 Day 15 predose, and 2 and 6 hours after dosing, Cycle 2 Day 1 and Cycle 3 Day 1 predose, predose at every other cycle (eg, Cycle 5, 7, etc.), at disease progression, and at the EOT Visit. All predose samples must be collected within 60 minutes before dosing and all post dose samples must be collected ± 30 minutes of the nominal time point. An unscheduled PK sample may be taken at the time of the onset of a new suspected, treatment-related adverse event when requested by the Sponsor.

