20. Archival tumor tissue samples will be collected at screening as long as no anticancer therapy was administered since the sample was collected. Fresh tumor tissue sample will only be collected if a patient qualifies for the study based on all other entry criteria and archival tissue is not available or not collected after the last anticancer therapy.

All Patients (optional): Additional tumor tissue samples may be collected for patients undergoing medical procedures including resection of metastases while on study or for patients that have disease progression if the patient consents and these samples will be used for further molecular testing of the cancer while treated with study drug.

21. CT scans of the pelvis, abdomen, and chest will be performed at screening (within 21 days of Cycle 1 Day 1). Subsequently, CT scans of the pelvis and abdomen will be performed every cycle through and including Cycle 4, and then every other cycle thereafter (ie, Cycle 6, 8, 10, etc.). CT scans of the chest will only be performed subsequently if the patient had lung metastases at screening or in case of lung symptoms (per the Investigator's discretion). Radiologic imaging may be performed up to 7 days prior to the corresponding study visit or post dose at the study visit. An initial indication of a partial or complete response based on investigator assessment must be confirmed ≥ 4 weeks later. MRI scans of the abdomen/pelvis and CT scan without contrast of the chest can be used for patients who are allergic to radiographic contrast media. Additionally, for patients whose local regulatory authority and/or ethics committee has not approved use of CT scans, MRIs may be used. Throughout the study, the same assessment technique must be used. Ultrasound scanning is not an acceptable substitute for CT scanning. See [Section 6.10.1](#) for further details.

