5.2. Study Drug Dose and Administration

Study drug may be dispensed only under the supervision of the Investigator or an authorized designee and only for administration to study patients. Patients will be randomized to receive 150 mg QD of DCC-2618 or placebo in repeated 28-day cycles.

The Investigator or designee must instruct the patient to take the study drug as per protocol.

- Patients should be instructed to take their assigned dose at the same time each day.
- Patients should take their study drug dose with a 6-ounce glass of water with or without food.
- Patients must be instructed to swallow the tablets whole. Tablets must not be crushed, chewed, or dissolved in liquid or food.
- The date, amount taken, and time of study drug administration must be recorded for the 3 days prior to PK sample collections and on the days of PK sample collection.
- On days of scheduled visits, the dose of study drug must be administered at the site after pre-dose assessments have been completed. The date, amount taken and time of study drug administration must be recorded.

If a patient dose escalates to 150 mg BID of DCC-2618, the Investigator or designee must instruct the patient to take the study drug as per protocol.

- Patients should be instructed take the study drug twice a day, at least 6 hours apart, and at the same time each day.
- Patients should take their study drug dose with a 6-ounce glass of water with or without food.
- Patients must be instructed to swallow the tablets whole. Tablets must not be crushed, chewed, or dissolved in liquid or food.
- The date, amount taken, and time of study drug administration must be recorded for the 3 days prior to PK sample collections and on the days of PK sample collection.
- On days of scheduled visits, the dose of study drug must be administered at the site after pre-dose assessments have been completed. The date, amount taken and time of study drug administration must be recorded.

If a patient forgets to take a dose at the scheduled time, the patient can take the scheduled dose if taken within 8 hours of the scheduled time that was missed for QD dosing and within 4 hours of the scheduled time that was missed for BID dosing. If more than 8 hours (for QD dosing) or 4 hours (for BID dosing) have passed after the scheduled time, then that missed

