5.10.1. Blinding

The patients and all site personnel, including the Investigator, the site monitor, and the study team must be blinded, with the exception of the following:

- Any site personnel for whom this information is important to ensure the safety of the patient in the event of a life threatening medical emergency
- Any site personnel for whom this information is important to ensure the safety of the patient and their fetus in the event of a pregnancy
- Vendors responsible for pharmacovigilance and regulatory personnel at the Sponsor to satisfy serious adverse event (SAE) processing and reporting regulations
- Clinical Supply Chain
- Unblinded statistician and programmer preparing the final (production) randomization list and unblinded analyses for the independent data monitoring committee (IDMC)
- IDMC
- Vendors analyzing PK and biomarker samples
- Vendor conducting the population PK analysis
- IRT vendor

- The Investigator, patient, site personnel, site monitor and study team will become unblinded to a specific patient's treatment assignment, if the patient has disease progression based on independent radiologic review.

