Confirmation of No Disease Progression: If the independent radiologic reviewer confirms that there is no disease progression, the patient will continue to receive study drug unless there is a medical need (ie, rapid progression or clinical deterioration) that requires the study drug to be discontinued. If the Investigator determines progression based upon clinical deterioration, a scan must be performed and reviewed by the independent radiologic reviewer to determine if the patient progressed. The basis for determination of progression per clinical deterioration must be documented in the patient's source documents and eCRF.

Confirmation of Disease Progression: Following confirmation of disease progression by modified RECIST based on independent radiologic review, the patient's treatment assignment will be unblinded via the IRT.

- **Patients randomized to DCC-2618 150 mg QD** will be given the option continue at an increased dose of 150 mg BID, to continue treatment on study with the same dose if the

Investigator feels the patient is receiving benefit from DCC-2618, or discontinue DCC-2618. If a patient continues treatment at the same dose, dose escalation is not allowed at a future time. At the time of dose escalation, the patient must come back to the site for study drug to be dispensed.

- **Patients randomized to placebo** will be given the option to cross over to receive DCC-2618 150 mg QD, or discontinue the study. Crossover patients must follow the schedule of assessments in [Table 2](#).

Confirmation of Disease Progression Following Crossover: Following confirmation of disease progression by modified RECIST based on Investigator review, patients will be given the option to dose escalate according to the rules in [Section 5.2.1](#), continue DCC-2618 at the same dose if the Investigator feels the patient is receiving benefit from DCC-2618, or discontinue DCC-2618. If a patient continues treatment at the same dose, dose escalation is not allowed at a future time. At the time of dose escalation, the patient must come back to the site for study drug to be dispensed.

More details on image acquisition guidelines and radiographic assessment will be provided in a separate protocol specific manual.

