8.3.5 Quality of Life

Quality of life (QOL) will be based on European Organisation for Research and Treatment of Cancer Quality of Life Questionnaire for Cancer 30-item (EORTC-QLQ-C30) and the EuroQol 5-Dimension 5-Level (EQ-5D-5L) questionnaires.

The EORTC-QLQ-C30 will be summarized by scale. In all scales, a high scale score represents a higher response level. The scoring for this questionnaire will be done in 2 steps.

1. Calculate the average of the items that contribute to the scale. This will be used as the raw score for the scale, and
2. Apply a linear transformation to standardize the raw score, so that scores range from 0 to 100.

Changes from baseline to Day 1 of Cycle 2 in EORTC-QLQ-C30 Role function and Physical function will be compared between the two treatment arms using analysis of covariance (ANCOVA) model with the stratification factors as factors. If Day 1 of Cycle 2 value is missing, then the change from baseline to the end of initial study treatment will be used in the analysis.

The EQ-5D-5L is a standardized measure of health status comprised of a descriptive system including five health-related QOL states (ie, mobility, self-care, usual activities, pain/discomfort, and anxiety/depression) and a visual analogue scale (VAS) of overall health. Each dimension is rated on a 5-point response scale indicating severity of problems, where 1 is “no problems”, 2 “slight problems”, 3 “moderate problems”, 4 “severe problems”, and 5 is “extreme problems”. The five questions are scored and together contribute to the EQ-5D-5L index (utility) score between 0 and 1 (1 being perfect health), which will be calculated using the developers’ algorithm based on country-specific reference score sets (Van Hout et al., 2012). Score sets are available for Denmark, France, Germany, Japan, Netherlands, Spain, UK, US and Zimbabwe. For countries in which no score set exists (Canada, Hungary, Israel, Romania, and Sweden) the closest neighboring country will be used as a proxy (EuroQol Group, 2015), eg, UK value set for Australia, France value set for Belgium, USA value set for Canada and Singapore, and Germany value set for Poland. If scale is missing for one of the dimensions, the index (utility) score will have a missing value.

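### Nothing requires the Cycle 2 Day 1 questionnaire to be completed before a patient with reviewed progression is told the assignment, so a step-4 QOL endpoint can be answered unblinded.

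*Protocol*

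**What the plan says.** **Scan timing.** Protocol Table 1 note 21 states that "CT scans of the pelvis and abdomen will be performed every cycle through and including Cycle 4", and Protocol 5.2 sets 28-day cycles. The first on-study scan therefore goes with Cycle 2 Day 1, nominal Day 29. The same note, repeated in Protocol 6.10.1, adds: "Radiologic imaging may be performed up to 7 days prior to the corresponding study visit or post dose at the study visit".

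**Unblinding.** Protocol 6.10.1: "Following confirmation of disease progression by modified RECIST based on independent radiologic review, the patient's treatment assignment will be unblinded via the IRT". Protocol 5.10.1 includes the patient: "The Investigator, patient, site personnel, site monitor and study team will become unblinded" when independent review shows progression. No waiting time is given.

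**Questionnaire timing.** Under Protocol Table 1 note 16 and Protocol 6.6.1, the "questionnaires must be performed before the patient sees the Investigator or designee on the day of the scheduled visit". If imaging is done within 7 days of the visit and the patient does not see the Investigator or designee, no questionnaire is needed on the imaging day.

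**Analysis.** SAP 8.3.5: "Changes from baseline to Day 1 of Cycle 2 in EORTC-QLQ-C30 Role function and Physical function will be compared between the two treatment arms". A missing Cycle 2 Day 1 value is replaced by the change to the end of initial study treatment. Protocol 9.6 and SAP 8.5 place the two scales fourth in the sequence, at 0.025 each, after PFS, ORR and OS.

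**Analysis period.** SAP 3.1 ends the double-blind period for a placebo patient who crosses over on the day before the first DCC-2618 dose, not on the date of unblinding.

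**The concern.** Role and Physical function are self-reported. A patient who has just learned of placebo and of progression may rate function differently from one who is still blinded. Early progression is expected far more often on placebo, so the effect would fall mainly on one arm. If knowing the assignment worsens the answers, the comparison is tilted towards DCC-2618.

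Neither the protocol nor the SAP prevents or detects this. The questionnaire rule is anchored to Investigator contact, not to the scan result or the disclosure. The ANCOVA does not distinguish forms completed before and after unblinding. The fallback points the same way: a placebo patient who is unblinded early may move to the crossover schedule without a Cycle 2 Day 1 form on initial treatment. The value used instead is then an end-of-treatment value, which may also follow unblinding.

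**Working it through.** **1. The sequence the documents allow**

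| Step | Source | Nominal timing |
|---|---|---|
| First on-study scan | Protocol Table 1 note 21, 6.10.1 | from Day 22 (29 − 7) to Day 29 |
| Independent read | Protocol 6.10.1 | turnaround not stated |
| Unblinding, patient included | Protocol 5.10.1, 6.10.1 | after reviewed progression, no minimum delay |
| EORTC-QLQ-C30 | Protocol Table 1 note 16, 6.6.1 | Day 29, before Investigator contact |

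The sequence breaks in two cases.
- The patient sees the Investigator at the early scan. The rule then implies that the form is done that day, before any central read.
- The scan is done on the visit day. It is then post dose, while Table 1 note 1 makes assessments predose unless otherwise specified, so the form comes first.

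What remains is an early scan without Investigator contact, followed by disclosure before the visit.

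**2. Planning model, checked against the plan's own figure**

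Inputs from Protocol 9.1: median PFS 4.5 and 1 month, 70 and 35 patients, accrual A = 9 months, further follow-up F = 6 months. With exponential PFS and λ = ln 2 / median:

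P(event) = 1 − [exp(−λF) − exp(−λ(A+F))] / (λA)

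- DCC-2618: 0.785 × 70 = 55.0
- Placebo: 0.9975 × 35 = 34.9
- Total 89.9, against the stated 90 (55 and 35). The figure is reproduced.

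**3. Ceiling on the share affected at Cycle 2 Day 1**

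A Day 22 scan falls 21 days after Day 1. With 30.44 days per month:

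- Placebo: 1 − 2^(−21/30.44) = 38.0%, or 15.2 of 40
- DCC-2618: 1 − 2^(−21/(4.5 × 30.44)) = 10.1%, or 8.1 of 80

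The ratio is 38.0/10.1 = 3.8. Three days either way (18 or 24 days) gives 34% to 42% on placebo and 9% to 11% on DCC-2618. These are PFS events, so they include deaths, and a patient who has died completes no form. To reach the ceiling, every patient would have to be scanned on the earliest day without seeing the Investigator, and be read and told before Day 29.

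**4. What it could do to the test (assumptions, not document figures)**

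Let f be the fraction of the 15.2 placebo progressors told before the form. Let s be the worsening in SD units due to knowing. Assume no shift on DCC-2618 and no true effect.

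Bias = 0.380 × f × s. SE = √(1/40 + 1/80) = 0.194. Critical value at two-sided 0.025 = 2.241.

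| f | Placebo patients told first | Rejection rate per scale, s = 0.25 to 1.0 |
|---|---|---|
| 10% | 1.5 | 0.025 to 0.028 |
| 25% | 3.8 | 0.026 to 0.043 |
| 50% | 7.6 | 0.029 to 0.105 |
| 100% | 15.2 | 0.043 to 0.390 |

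At 10% the effect is negligible against the nominal 0.025. The bottom row is the unrealistic extreme described in step 3.

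**The case against.** The strongest objection is that the size rests on documents not available here. Protocol 6.10.1 leaves imaging procedures to a review charter and a separate manual, and Protocol 5.11 leaves IRT unblinding instructions to the Study Reference Manual. Read times, or an order of events, may be fixed there, and the number affected could be zero. This stands as a limit on size. It does not remove the point, because the blinding of a formally tested endpoint should not depend on an unstated turnaround.

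Existing rules also narrow the gap. A form is implied at an early scan if the Investigator is seen, and on the visit day the form precedes that contact. SAP 3.1 ends the double-blind period at the progression date for DCC-2618 patients who continue at the same dose. For placebo patients who cross over, it leaves only the interval from unblinding to the day before the first crossover dose. All of this stands, and disclosure between an early scan and the visit remains possible.

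Unblinding at progression is deliberate: it supports the crossover that answers the ethical concern in Protocol 1.4.1. That stands too. The point concerns only the order of form and disclosure.

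A reader might extend the ceiling to Day 29 itself, 28 days elapsed, which gives 47% and 13%. The documents do not support this, because a visit-day scan is post dose and the questionnaires are predose. A reader might also infer that the QOL result is biased. The documents show only that the sequence is permitted, not that it occurs.

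**Conclusion.** The gap is real but minor. The documents allow scan, read, disclosure and then questionnaire for a patient who does not see the Investigator at an early scan, and the fallback value has the same weakness. The share affected is unknown. It lies between about zero and a ceiling of roughly 38% on placebo and 10% on DCC-2618. That ceiling rests on exponential PFS at the planning medians, nominal visit timing and the earliest permitted scan, and it counts deaths.

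The imbalance between arms is better supported than the size: about 3.8 to 1 under the planning assumptions. Any consequence is confined to the QOL step, and it bears on confirmatory inference only if PFS, ORR and OS are all significant. PFS by independent review is not affected. The case for acting is that prevention is cheap and that the plan would not currently show whether the problem had occurred.

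**What to change.** **Protocol 6.6.1 and 6.10.1.** State that once independent review shows progression, the due questionnaires (Cycle 2 Day 1 or end of initial treatment) are completed on the site tablet before the assignment is disclosed to the patient.

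**SAP 8.3.5.** Report by arm the number of Cycle 2 Day 1 forms and fallback forms dated after the IRT unblinding date. A repeat ANCOVA without those forms may be shown, but as descriptive only. It selects on progression, removes mostly placebo patients who have progressed, and cannot separate knowledge of the assignment from the effect of progression on function. A changed result would therefore not establish unblinding bias, and an unchanged one would not exclude it.

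**Cost.** Procedure wording, one date comparison and a small procedural burden at sites. Some forms will be completed a few days before the nominal visit. The treatment options after progression are not changed.

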1. INTRODUCTION AND RATIONALE

[figure not shown]
1.1. Introduction

Activating mutations in the receptor tyrosine kinases KIT or PDGFRA have been identified in multiple cancer types such as gastrointestinal stromal tumors (GIST), subsets of melanoma, testicular seminomas and acute myeloid leukemia (AML), and in myeloproliferative neoplasms such as systemic mastocytosis (SM) that include aggressive SM (ASM) and mast cell leukemia (2, 3, 4, 5, 6). In addition, aberrant wt KIT and/or PDGFRA overexpression is found in GIST, melanoma, AML, gliomas and neuroendocrine tumors (7, 8, 9, 10).

Most gastrointestinal stromal tumors are driven by activating mutations in KIT (~80%) or the related PDGFRA (~10%) receptor tyrosine kinases (1, 23). In GIST patients at presentation, mutations in the KIT gene are usually found in exon 9 or 11. Primary mutations in exon 11 disrupt the auto-inhibited form of the kinase, and those in exon 9 increase receptor dimerization. Both mechanisms cause ligand-independent receptor activation, which leads to uncontrolled cell growth and transformation. Several KIT-targeted therapies have been approved for the treatment of GIST, but there are limitations to their therapeutic success.

Upon treatment with targeted therapies, secondary resistance mutations in KIT usually arise in the catalytic domain of the kinase, and frequently these mutations map to the embedded conformational switch control mechanism that regulates KIT activity (Figure 2). Secondary mutations in KIT typically occur in exons 13 and 14 (near the adenosine triphosphate (ATP)-binding pocket) that sterically disrupt drug binding or conformationally activate KIT, and in the activation loop (conformation-controlling switch) encoded by exons 17 and 18 (11, 12). Activation loop mutations act by shifting the kinase into an activated conformation that is less amenable to drug binding by any of the approved therapies (13). Other diseases that have primary mutations in the KIT (or PDGFRA) activation loop include SM, AML, and PDGFRA-driven GIST (7, 14, 15).

Figure 2: Multiple Secondary KIT Mutations in Gastrointestinal Stromal Tumor Patients Span Exon Regions 13-18

Source: Liegl B, Kepten I, Le C, Zhu M, Demetri GD, Heinrich MC, et al. Heterogeneity of kinase inhibitor resistance mechanisms in GIST, *J. Pathol.* 2008 Sep;216(1):64-74.

Imatinib was the first KIT inhibitor approved as a therapy for advanced GIST in 2002 (16). Imatinib therapy is usually not curative in unresectable and/or metastatic disease with complete responses (CRs) seen in ~5% of patients and an objective response rate (ORR) of 68% (17). More than 80% of GIST patients will receive clinical benefit from imatinib monotherapy, but as development of imatinib-resistance is essentially inevitable, more than half will develop progressive disease by 2 years (18). Progression is largely due to secondary mutations in the KIT kinase domain that cause resistance to imatinib (12). Although imatinib is effective against exon 11 mutations in KIT, and has some efficacy against exon 9 mutations when the dose is increased to 800 mg, little to no response to imatinib is seen for other mutations in KIT and PDGFRA, particularly those that mediate the conformational dynamics of switch activation (18, 19).

Sunitinib was approved in 2006 as a second-line therapy for GIST patients who had disease progression on or intolerance to imatinib. Sunitinib has greater activity against exon 9 mutations compared to imatinib and less activity against exon 11 mutations (15, 18). Additionally, sunitinib shows activity against KIT exon 13 and 14 mutations, but only half the patients show benefit and median progression-free survival (PFS) is 5.5 months (18). Sunitinib is not effective against KIT exon 17/18 and PDGFRA exon 18 activation loop mutations.

Regorafenib was approved in 2013 as a third-line therapy for adult patients with metastatic and/or unresectable GIST who have had disease progression on or intolerance to imatinib and sunitinib treatment. In addition to being active against KIT exon 11 mutations, regorafenib is the only approved therapy with activity against a subset of exon 17 mutations in KIT and for patients who respond, PFS approaches 5 months. Some patients present with mutations in KIT that are not effectively treated by regorafenib, and additionally, other or multiple secondary mutations arise and cause resistance to therapy (12). Tumor heterogeneity has been found with multiple secondary mutations in KIT arising within an individual patient in different areas of 1 tumor or distinct sites of metastasis (12).

The complex heterogeneity of KIT mutations within individual patients is a major cause of resistance to therapy (12). A kinase inhibitor that could broadly inhibit clinically relevant KIT mutations or multiple mutations in KIT within an individual GIST patient could be of high therapeutic value in the treatment of refractory GIST patients. Importantly, determining whether such an inhibitor could delay development of resistance mutations within KIT is an important therapeutic objective with DCC-2618.

At present, there are no approved targeted therapies that broadly inhibit secondary drug-resistant mutations in GIST. Thus, a high medical need remains for developing kinase inhibitors that are effective against these mutant forms of KIT and PDGFRA.

